10.3. Criteria for Potentially Clinically Significant Values (PCSV)

Parameter	PCSV	Comments
Potassium	<3 mmol/L and baseline ≥ 3 mmol/L ≥5.5 mmol/L and baseline < 5.5 mmol/L	FDA Feb 2005. Two independent criteria
Triglycerides	\geq 4.6 mmol/L and < 4.6 mmol/L at baseline	Threshold for therapeutic intervention.
Glucose Hypoglycaemia	\leq 3.9 mmol/L and \leq LLN and baseline $>$ 3.9 mmol/L or \geq LLN \geq 11.1 mmol/L (unfasted); \geq 7 mmol/L (fasted) and baseline \leq	ADA Jan 2008.
Hyperglycaemia	mmol/L (fasted)	
Albumin	\leq 25 g/L and >25 g/L at baseline	
Hematology		
WBC	<3.0 Giga/L and ≥3.0 Giga/L at baseline (Non-Black); <2.0 Giga/L and ≥2.0 Giga/L at baseline (Black) ≥16.0 Giga/L and ≤ 16 Giga/L at	Increase in WBC: not relevant. *The default criteria. Summary by race (black and Non-black) are optional.
	baseline	To be interpreted only if no differential count available.
Lymphocytes (ALC)	>4.0 Giga/L and ≤4.0 Giga/L at baseline	
Neutrophils	<1.5 Giga/L and ≥1.5 Giga/L at baseline (Non-Black); <1.0 Giga/L and ≥1.0 Giga/L at baseline (Black)	International Consensus meeting on drug-induced blood cytopenias, 1991. *The default criteria. By race (black and Non-black) are optional.
Monocytes	>0.7 Giga/L and \leq 0.7 Giga/L at baseline	
Basophils	>0.1 Giga/L and \leq 0.1 Giga/L at baseline	
Eosinophils	(>0.5 Giga/L and >ULN) and (\leq 0.5 Giga/L or \leq ULN at baseline)	Harrison- Principles of Internal Medicine 17th Ed., 2008.
Hemoglobin	≤ 115 g/L and > 115 g/L at	Three criteria are independent.
	baseline for male; \leq 95 g/L and 95 g/L at baseline for Female. \geq 185 g/L and $<$ 185 g/L at	*The default criteria. By gender (male and female) are optional.
	baseline for Male; ≥ 165 g/L and < 165 g/L at baseline for Female Decrease from Baseline ≥ 20 g/L	Criteria based upon decrease from baseline are more relevant than based on absolute value. Other categories for decrease from baseline can be used (\geq 30 g/L, \geq 40 g/L, \geq 50 g/L).
Hematocrit	$\leq 0.37 \text{ v/v}$ and $> 0.37 \text{ v/v}$ at baseline for Male ; $\leq 0.32 \text{ v/v}$ and > 0.32 v/v at baseline for Female $\geq 0.55 \text{ v/v}$ and $< 0.55 \text{ v/v}$ at baseline for Male ; $\geq 0.5 \text{ v/v}$ and < 0.5 v/v at baseline for Female	Two Criteria are independent *The default criteria. By gender (male and female) are optional.

Parameter	PCSV	Comments
RBC	<4 Tera/L and ≥ 4 Tera/L at baseline for Male; <3 Tera/L and ≥ 3 Tera/L at baseline for Female ≥ 7 Tera/L and <7 Tera/L at baseline for Male; ≥ 6 Tera/L and <6 Tera/L at baseline for Female	Unless specifically required for particular drug development, the analysis is redundant with that of Hb.
Platelets	<100 Giga/L and ≥100 Giga/L at baseline ≥700 Giga/L and < 700 Giga/L at baseline	International Consensus meeting on drug-induced blood cytopenias, 1991. Two independent criteria
Vital signs		
HR	\leq 50 bpm and decrease from baseline \geq 20 bpm \geq 120 bpm and increase from	
SBP	≤95 mmHg and decrease from baseline ≥20mmHg ≥160 mmHg and increase from baseline ≥20 mmHg	
DBP	≤45 mmHg and decrease from baseline ≥10 mmHg ≥110 mmHg and increase from baseline ≥10 mmHg	
Respiratory rate	< 12 per minutes and ≥12 per minute at baseline >20 per minute and ≤20 per minute at baseline	

10.4. Search Criteria for TEAE of Special Interest

AESI	Search Criteria
Systemic or severe hypersensitivity reactions	Narrow SMQ for hypersensitivity Note: manual adjudication of relevant PTs will be required by the study medical monitor, before database lock
Severe injection site reactions	HLT=Injection Site Reactions AND Serious AE= "Yes" OR Severity= "severe"

Signature Page for VV-RIM-00163457 v1.0 Approved

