#### **10.1.3.** Events that Require Expedited Reporting to Sponsor

The following events also require reporting to the Sponsor (or designee) within 24 hours of learning of the event:

- SAEs
- Selected Adverse Events of Special Interest (AESI; serious and nonserious): Adverse events of special interest for this study include systemic or severe hypersensitivity reactions and severe injection site reactions.
- **Pregnancy:** Although pregnancy is not considered an AE, it is the responsibility of the investigator to report to the Sponsor (or designee), within 24 hours of identification, any pregnancy occurring in a female or female partner of a male, during the study or within 6 months of the last dose of study drug. Any complication of pregnancy affecting a female study subject or female partner of a male study subject, and/or fetus and/or newborn that meets the SAE criteria must be reported as an SAE. Outcome for all pregnancies should be reported to the Sponsor.

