4.6.2. Adverse Events of Special Interest

Adverse events of special interest (AESI) for this study include systemic or severe hypersensitivity reactions and severe injection site reactions.

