6.3. Data Handling Convention for Missing Data

Missing data will not be imputed in listings. This section includes the methods for missing data imputation for some summary analyses, if necessary.

Rules for handling missing data for primary and secondary efficacy variables are described in Section 4.5.1 and Section 4.5.2.

Adverse event

If the intensity of a TEAE is missing, it will be classified as "severe" in the frequency tables by intensity of TEAEs. If the assessment of relationship of a TEAE to the investigational product is missing, it will be classified as related to the investigational product.

Adverse event start date

AE start date will be used for AE classification and analysis of AESIs. If AE start date is not complete, then the character variable will keep the original incomplete date, the numerical date variable will be imputed, and an imputation flag will be used to indicate which date component is missing.

If AE start day is missing, and AE start month and year are not missing: If AE start year is the same as first dose year and AE start month is the same as first dose month, then AE start day will be imputed using the day of first dose. If this leads to a date after the AE end date, AE end date will be used instead. If AE start year is the same as first dose year and AE start month different from first dose month, AE start day will be imputed using the first day of the month. If this leads to a date before informed consent date, the informed consent date will be used. Imputation flag is 'D'.

Regeneron Pharmaceuticals, Inc. Statistical Analysis Plan

If AE start month is missing, and AE start year is not missing: If AE start year is before the first dose year, the informed consent day and month will be used. If AE start year is the same as first dose year, the first dose day and month will be used. If this leads to a date after AE end date, AE end date will be used instead. If AE start year is after the first dose year, January 1st will be used. Imputation flag is 'M'.

If AE start year is missing: The date of first dose will be used. If this leads to a date after the AE end date, AE end date will be used instead. Imputation flag is 'Y'.

Adverse event end date

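### The SAP's search rule for severe injection site reactions lacks brackets around its OR, so read literally it selects every TEAE graded severe, whatever its HLT.

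*SAP*

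**What the plan says.** SAP 10.4 is titled "Search Criteria for TEAE of Special Interest", so the events searched are TEAEs. For the row on severe injection site reactions the criterion is "HLT=Injection Site Reactions AND Serious AE" equal to Yes, followed by OR severity equal to severe. It contains one AND and one OR, and nothing shows how they group.

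The definition that this search should implement is the same in both documents. SAP 4.6.2 states: "Adverse events of special interest (AESI) for this study include systemic or severe hypersensitivity reactions and severe injection site reactions". Protocol 10.1.3 says the same when it lists events for expedited reporting.

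SAP 5.7.1 plans a table of AESIs by category, broken down by SOC, HLT and PT, and refers to section 10.4 for the categories. SAP 8 names SAS 9.4 or above as the software. The hypersensitivity row of SAP 10.4 adds that "manual adjudication of relevant PTs will be required by the study medical monitor, before database lock". The injection site reaction row has no such note.

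**The concern.** The rule in SAP 10.4 is what a programmer would be given to build the AESI table. Without brackets, AND binds before OR, in SAS as elsewhere. The HLT restriction then applies only to the serious branch, and the severity branch stands alone. A severe event with no connection to the injection would meet the criterion and be counted as a severe injection site reaction.

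At stake is whether one row of a planned safety table can be trusted. If the rule is coded as written, the count in that row no longer measures what its label says. No review step is stated for that row that would remove the unrelated events.

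**Working it through.** The plan gives no figure to reproduce here. The check is a truth table, followed by a scale illustration.

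**Inputs.** The criterion comes from SAP 10.4, the definition from SAP 4.6.2 and Protocol 10.1.3, and the 150 subjects per arm from SAP 2.3.

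**Step 1: three readings.** Let H mean that the HLT is injection site reactions, S that the event is serious, and V that it is graded severe.

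- Literal: (H AND S) OR V. Strict left-to-right evaluation gives the same expression.
- Bracketed: H AND (S OR V).
- Definition taken at its word: H AND V.

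| H | S | V | Literal | Bracketed | Definition |
|---|---|---|---|---|---|
| no | no | no | – | – | – |
| no | no | yes | selected | – | – |
| no | yes | no | – | – | – |
| no | yes | yes | selected | – | – |
| yes | no | no | – | – | – |
| yes | no | yes | selected | selected | selected |
| yes | yes | no | selected | selected | – |
| yes | yes | yes | selected | selected | selected |

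The literal rule selects 5 of the 8 combinations. Two of those 5 are not injection site reactions: severe events with another HLT, serious or not. The bracketed rule selects 3, all of them injection site reactions. The definition selects 2. The bracketed rule and the definition differ in one combination, an injection site reaction that is serious but not severe.

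**Step 2: scale.** The documents give no rate of severe TEAEs, so the rate p of subjects with a severe TEAE outside the injection site HLT is an assumption. Subjects misplaced per arm = p × 150:

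- p = 1%: 0.01 × 150 = 1.5
- p = 3%: 0.03 × 150 = 4.5
- p = 5%: 0.05 × 150 = 7.5

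**Step 3: how small is the true count?** Protocol 3.2.3 reports that all treatment-related TEAEs in Part B of the first-in-human study were mild or moderate. Protocol 3.3 gives 32 birch-allergic subjects treated. By the rule of three, no severe treatment-related event in 32 subjects is compatible with a true rate up to about 3/32 = 9.4%, and 0.094 × 150 is about 14 per arm. A low true count is plausible, but the documents do not establish that it is near zero.

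**Step 4: missing intensity.** SAP 6.3 says "If the intensity of a TEAE is missing, it will be classified as" severe, but limits this to the frequency tables by intensity. Events with missing intensity enter the search only if that derived variable is reused for it, and the SAP does not say whether it is.

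**The case against.** The strongest reply is that the intent is not in doubt. The row label and both definitions restrict this AESI to injection site reactions, the cell is a specification and not program code, and a careful programmer would probably supply the brackets. An error would also be visible: the AESI table is split by SOC, HLT and PT, so an unrelated event would appear under its own HLT inside a category named for injection site reactions. The text reviewed was read from a PDF, and a lost line break might have suggested the grouping.

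Most of this stands, and it is why the point is minor. It does not make the rule correct. A pre-specified search should not depend on the programmer departing from it, and a line break is not a bracket. SAP 10.3 brackets some mixed and/or criteria (eosinophils, for example) but not the hypoglycaemia one, so the appendix has no convention that settles the reading.

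A reader might infer more than the documents support:

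- *That injection tolerability as a whole would be misreported.* It would not. SAP 5.7.1 separately summarises injection site reactions by PT and TEAEs by severity, and SAP 5.10.2 uses the HLT alone for the immunogenicity comparison. None of these uses the faulty search.
- *That every severe adverse event is captured.* The section title limits the search to TEAEs.
- *That events with missing severity are certainly captured.* The SAP 6.3 rule is written for the intensity tables only.
- *That nearly all entries in the row would be wrong, or that a difference between arms would be hidden or created.* With no severe-TEAE rate and only 32 treated birch-allergic subjects behind the expected true count, neither the proportion nor the direction can be stated.

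**Conclusion.** The point holds as a drafting error in an operative safety rule. Followed literally, SAP 10.4 places every severe TEAE in the row for severe injection site reactions, against the plan's own definition. The illustrated range of about 1.5 to 7.5 misplaced subjects per arm rests entirely on the assumed rates of 1% to 5% and on all 150 subjects per arm being in the safety set. Severity is low: the intent can be recovered from the label, the table layout would help expose a miscoding, and the other injection site summaries and all efficacy analyses are untouched.

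**What to change.** In SAP 10.4, group the last two conditions: `HLT = Injection Site Reactions AND (Serious AE = Yes OR Severity = severe)`.

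In the same edit:

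- State whether serious but non-severe injection site reactions are meant to count. If they are, adjust the row label and the definition in SAP 4.6.2 to say so. If not, drop the serious condition.
- State whether a missing intensity counts as severe for this search.

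The cost is one pair of brackets and two clarifying sentences. No new data are needed and no hypothesis test changes. The edit should be made before database lock and unblinding.
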